Ventricular tachycardia is less common, and relative bradycardia is an ominous sign, with bradyarrhythmias frequently observed in the setting of cardiopulmonary arrest. Clinical studies of defibrillator/pacemaker therapy for primary prevention against sudden death in PAH patients are lacking.

D. Heart rate variability

As PH progresses, the RV afterload increases, ultimately leading to impaired cardiac output and right-side heart failure. Consequently, the sympathetic nervous system activity (SNS) increases and the parasympathetic nervous system (PNS) decreases [12, 18]. The autonomic nervous system (ANS) regulates the sinus node, and can be assessed by heart rate variability (HRV) [19, 20]. The HRV illustrates the autonomic balance between the sympathetic and parasympathetic input, and is a noninvasive indicator of the autonomic input to the heart [21].

Reveal LINQ Insertable Cardiac Monitor

The Reveal LINQ Insertable Cardiac Monitor is a wireless and the smallest insertable cardiac monitor. The Reveal LINQ insertion procedure is minimally invasive, and requires short procedure time and clinical resources. It is placed under the skin of the chest and automatically detects and records abnormal heart rhythms for up to 3 years.

Figure 2. The Reveal LINQ Insertable Cardiac Monitor is supported by a CareLink Network and a patient monitor easy to use that features cellular technology. Alert notifications can result in earlier

ASPIRE: ArrhythmiaS in Pulmonary arterial hYPERtension and right heart failure assessed by continuous long-term cardiac monitoring

clinical decisions compared to non-wireless devices (21). The Reveal LINQ is safe for use in an MRI setting.

CareLink® Remote Monitoring Network

The Medtronic CareLink Network ensures timely identification of clinically important issues, such as asymptomatic atrial fibrillation or device integrity issues (22). Data are automatically sent to the CareLink server from the device. In addition, patients can transmit device information from home (Figure 3), and clinicians can review device data when and where they choose on the Medtronic CareLink Clinician Website. The Medtronic CareLink Network provides comprehensive data comparable to an in-clinic device check, including full parameter summary, A-V conduction histograms and arrhythmia summary.

[figure not shown]

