Selection criteria	
Inclusion criteria:
 
The following patients will be included in the study:
 
 - Patients >18 years of age - Patients on current PAH specific medication must be stable for at least 3 months. - Patients can be included in WHO group 1 only with IPAH or CTD-aPAH and group IV, CTEPH 
Exclusion Criteria:
 
 - Patients who are unlikely to comply with the study protocol and procedures required by the study protocol. - Patients with any severe complication or comorbidity other than PAH which might determine the prognosis and functional level of the patient. - Need for escalation of PAH specific therapy - Patients who are already in specific treatment for arrhythmias. 
Concomitant treatments
 
 - Patients can be on the following treatments only if they have been at least treated for three months prior to inclusion and are planned to be continued during the whole study period: diuretics, digoxin, beta-blockers and amiodarone
Data collection	
At screening:
 
 - PAH verified with right heart catheterization before start of PAH specific medication. - Basic demographic data including medication. - Physical examination and vital signs - 6 MWT - Digital ECG to verify rhythm at baseline 
Care Link Network
 
 - Device information send from home - Clinicians review device data on the Medtronic CareLink Clinician Website 
Visits every 6 months
 
 - 6 MWT - Lab tests, including NT-proBNP - Record concomitant medications
Statistical methods	
SPSS/PASW Statistics 19 software (SPSS Inc, Chicago IL), SAS or R are used for all statistical analyses.
 
In addition, descriptive time serial analysis will be done on heart rate variability and heart rate.
 
Correlation statistics will be done to assess heart rate variability and heart rate in correlation to known risk markers in PH.

Endpoints	To assess the incidence of arrhythmias in patients with PAH.

Study Chart - ASPIRE I

	Screening	Operation	Visit 1	Visit 2	Visit 3	Visit 4
Informed consent	X	1	6 mo	12 mo	18 mo	24 mo
Height	X					
Weight	X					
RHC ^a	X					
SPECT/CT	X					

ASPIRE: ArrhythmiaS in Pulmonary arterial hYPERtension and right heart failure assessed by continuous long-term cardiac monitoring

LFT	X					
ECG	X	x	X	X	x	X
Echocardiography	X			x		x

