Optimization of specific therapy in PAH using continuous long-term arrhythmia monitoring

Background

In most cases, onset of atrial tachyarrhythmias is related to clinical deterioration, and deterioration in exercise capacity by one functional class or more, and development of ascites and/or edema refractory to diuretic therapy (37). Restoration of normal sinus rhythm is invariably associated with clinical improvement. The onset of these arrhythmias could be a warning sign for deteriorating RV function and hence the need for increasing specific therapy for PAH. Although prospective and controlled data are lacking, these findings suggest that maintenance of sinus rhythm is an important treatment goal in patients with PAH, which contrasts with the clinical experience in left heart failure in non-PAH patients, where the rhythm control strategy seems to offer no mortality benefit compared to the rate control and systemic anticoagulation strategy (38).

[figure not shown]

Figure 3: Kaplan-Meier estimates of survival in patients with PAH in relation to supraventricular arrhythmias (SVA; (7))

ASPIRE: ArrhythmiaS in Pulmonary arterial hypertension and right heart failure assessed by continuous long-term cardiac monitoring

With regard to mortality, while AVNRT and AFL were invariably converted to sinus rhythm and were not associated with an increased risk of death (cumulative mortality<6%), the presence of persistent atrial fibrillation and failure to restore sinus rhythm were associated with a cumulative mortality of > 80% (9). AF may be a particularly malignant arrhythmia in patients with chronic PAH and RHF (10).

In terms of ventricular arrhythmias QT prolongation increases the risk for VAs and especially for torsades-de-pointes tachycardia. QTc interval in PH patients are generally longer compared to controls (454.8 ± 29 ms vs. 429.8 ± 18 ms, $p < 0.001$) (16). A prolonged QTc interval correlated with deterioration of the RV, and when QTc was ≥ 480 ms an increased risk of death was observed in a multivariate analysis (HR=3.09 [CI 95%; 1.61-8.38], $p = 0.022$). Furthermore, an analysis of CPR outcome in PAH patients showed that several arrhythmias are indicative of imminent cardiac arrest. The outcome of CPR in PAH-patients was critical, with a survival rate of 6% after 90 days (12).

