Study design	Single centre observational study with CMR in newly referred and PAH patients treated with PAH-specific therapy. Patients will be followed for 2 years after inclusion.
Study objectives	
Primary objective
 
To evaluate long-term monitoring of arrhythmias as a predictor tool for escalation of PAH specific therapy and prognosis in patients with PAH.
 
Secondary objectives
 
 - To assess change in 6 MWT - To assess hemodynamic changes with RHC - To assess hemodynamic changes in echocardiography - To assess the number of patients progressing one FC (Modified NYHA class) - To assess changes in NT-proBNP. - To assess Hospital admission for any reason - To assess Death or transplantation
Methodology	The study will be conducted as a single center study at Copenhagen University Hospital, Rigshospitalet, DK-Denmark.
Trial duration	Enrollment duration: 9 months
Number of patients	40 patients. WHO Group I PAH: 10 with IPAH, 10 with CTD-aPAH, WHO Group III : 10 with pulmonary disease related PH and Group IV: 10 with CTEPH.
Selection criteria	
Inclusion criteria:
 
The following patients will be included in the study:
 
 - Patients >18 years of age - Voluntary participation after giving informed verbal and written consent - Patients untreated with PAH specific therapy - Patients on current PAH specific medication independent of duration of therapy - Patients can be included irrespective of pre-medication disease (WHO group 1) 
Exclusion Criteria
 
 - Patients who are unlikely to comply with the study protocol and procedures required by the study protocol. - Patients with any severe complication or comorbidity other than PAH which might determine the prognosis and functional level of the patient. 
Concomitant treatments
 
 - Patients can be on the following treatments only if they have been at least treated for three months prior to inclusion and are planned to be continued during the whole study period: diuretics, digoxin, beta-blockers and amiodarone

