Data collection	
At screening:
 
 - SPECT/CT will be performed at diagnosis for prevalent cases only and at screening for incident cases to exclude pulmonary embolism - LFT to exclude pulmonary disease: COPD and ILD - Echocardiography to exclude left heart disease - PAH verified with right heart catheterization before start of PAH specific medication - Basic demographic data including medication. - Physical examination and vital signs - 6 MWT - ECG - Lab tests including liver and renal function tests and NT-pro-BNP

ASPIRE: ArrhythmiaS in Pulmonary arterial hypertension and right heart failure assessed by continuous long-term cardiac monitoring

	
Visits every 6 months or with increased symptomatology
 
 - 6 MWT - Lab tests, including liver and renal function tests including yearly eGFR and NT-proBNP - Echocardiography yearly and at 3 month after inclusion - Record concomitant medications - PAH medications
Endpoints	
Primary endpoints
 
 - Arrhythmias as assessed by Insertable Cardiac Monitors 
Secondary endpoints
 
 - Modified NYHA functional class - Reduction in 6 MWT in the study period. - NT-proBNP change in study period. - Change and /or escalation of PAH therapy - Respiratory hospitalization - Death or transplantation
Statistical methods	SPSS/PASW Statistics 19 software (SPSS Inc, Chicago IL), SAS or R is used for all statistical analysis.

Study Chart – ASPIRE III

	Screening	Operation	Visit 1	Visit 2	Visit 3	Visit 4
		1	6 mo	12 mo	18 mo	24 mo
Informed consent	x					
Height	x					
Weight	x					
RHC [¤]	x					
SPECT/CT	x					
LFT	x					
ECG	x	x	x	x	x	x
Echocardiography	x			x		x
6 MWT	x	x	x	x	x	x
Clinical data collection	x	x	x	x	x	x
Blood Samples#	x	x	x	x	x	x

¤ RHC: right heart catheterisation for incident cases only. Prevalent cases have had RHC at the time of diagnosis. *CMR, cardiac index, RV size, stroke volume and pulmonary artery diameter including exercise measurements #Blood samples include haematology, liver chemistry (ALT, AST, LDH bilirubin) renal (creatinine, eGFR), and NT-proBNP.

Limitations

Reveal LINQ Insertable Cardiac Monitor, ICM

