The ICM used in this study is wireless and the smallest available device, and the insertion procedure is minimally invasive, and requires short procedure time and clinical resources. To be able to send device information from home cellular technology is required.

Cardiac magnetic resonance imaging, CMR

CMR has its own limitations. Unlike echocardiography, it is expensive and not widely available. Data acquisition and post-processing can be time consuming and the need for patients to lie flat in the scanner can be somewhat challenging. However, with improved technology, many of the parameters mentioned above can be attained in almost the same amount of time as a standard 2-dimensional echocardiography (2DE).

Conclusions and perspectives

Arrhythmias in pulmonary arterial hypertension and right heart failure are prominent problems with an incidence of up to 35%. Supraventricular arrhythmias are the most prevalent in patients with pulmonary arterial hypertension. Permanent atrial fibrillation is the most ominous supraventricular arrhythmias and at the same time the most difficult to treat, whereas transient episodes of supraventricular arrhythmias seem to have no effect on mortality. Right ventricular and atrial parameters correlate with an increased risk of supraventricular arrhythmias in idiopathic pulmonary arterial hypertension patients. Prolonged QTc is associated with an increased risk of death.

More data is needed to determine the optimal way to restore sinus-rhythm and manage arrhythmias in pulmonary arterial hypertension. In cases with atrial flutter, the most feasible and the safest therapy is radiofrequency ablation.

This is the first study to assess arrhythmias in a homogeneous patient population prospectively, equally distributed among the different subgroups of pulmonary arterial hypertension with long-term monitoring. The implantation of an Insertable Cardiac Monitor records the heart rhythm continuously, for up to three years, and saves ECG details immediately preceding and during arrhythmia. This approach in combination with MR scanning of RV haemodynamic parameters holds the promise for optimizing specific therapy in patients with PAH and right heart failure.

Risks and side effects

MR scan:

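### ASPIRE III: the link between monitored arrhythmia and escalation of PAH therapy may be partly self-fulfilling, because clinicians can see the recordings and the plan does not separate escalations by what prompted them

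*Combined protocol and SAP*

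**What the plan says.** The primary objective in the ASPIRE III synopsis is "To evaluate long-term monitoring of arrhythmias as a predictor tool for escalation of PAH specific therapy and prognosis in patients with PAH". Under Endpoints in the same synopsis, the primary endpoint is "Arrhythmias as assessed by Insertable Cardiac Monitors", which is the predictor in that objective. The escalation outcome, "Change and /or escalation of PAH therapy", is a secondary endpoint with no definition. The ASPIRE III Statistical methods entry names software and nothing else.

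On access to the predictor, the ASPIRE I synopsis (Data collection, Care Link Network) says "Clinicians review device data on the Medtronic CareLink Clinician Website". The general description of the CareLink network says that "clinicians can review device data when and where they choose on the Medtronic CareLink Clinician Website". The caption to Figure 2 begins "Alert notifications can result in earlier" and goes on to clinical decisions, in comparison with devices that are not wireless. No masking of device data is described.

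On the link to treatment, the Background to Project ASPIRE III says "The onset of these arrhythmias could be a warning sign for deteriorating RV function and hence the need for increasing specific therapy for PAH". Conclusions and perspectives says that monitoring combined with MR scanning "holds the promise for optimizing specific therapy in patients with PAH and right heart failure". The Limitations section discusses the device and CMR as techniques and does not raise this issue.

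**The concern.** Escalation is a decision, not a measurement. If the person deciding has seen the arrhythmia and regards it as a possible sign of worsening, the arrhythmia can bring about the outcome through that person. An association between arrhythmia and escalation then has two explanations: arrhythmia precedes disease that needs more therapy, or clinicians respond to what the monitor shows. Only the first supports the monitor as a predictor. The plan collects nothing specified that would tell them apart, and the reason for a treatment change is hard to recover reliably afterwards.

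**Working it through.** **Is the loop in the documents?**

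1. Outcome predicted: escalation, named in the ASPIRE III primary objective. Stated.
2. Predictor visible to clinicians: stated in the ASPIRE I synopsis and in the general CareLink description. The ASPIRE III Data collection entry does not repeat it, but its endpoint uses the same kind of monitor.
3. The clinicians who see the data also decide on escalation: not stated. It is inferred from the single-centre design (ASPIRE III synopsis), recruitment from the clinic's own treated cohort (Recruitment of patients) and the absence of masking.
4. Arrhythmia as a possible prompt: stated in the ASPIRE III Background as a possibility.
5. Anything that breaks the loop: the documents specify no escalation criteria, adjudication, recorded reason or separating analysis.

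**How large could it be?** The plan gives no escalation rate, effect size or power for ASPIRE III, so there is no figure of its own to reproduce; the sample is 4 × 10 = 40. What follows is an illustration.

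Assume arrhythmia carries no information about the need to escalate. Every patient has a 2-year escalation probability b. A clinician who sees an arrhythmia escalates an otherwise un-escalated patient with probability r. Both b and r are assumptions. Then

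- risk with arrhythmia = b + (1 − b) × r
- risk without arrhythmia = b
- spurious risk ratio = [b + (1 − b) × r] / b

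With b = 0.30 and r = 0.50: 0.30 + 0.70 × 0.50 = 0.65, and 0.65 / 0.30 = 2.17. The extremes of the grid are 0.55 / 0.40 = 1.375 (b = 0.40, r = 0.25) and 0.80 / 0.20 = 4.0 (b = 0.20, r = 0.75).

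| r | ratio, b = 0.20 | ratio, b = 0.30 | ratio, b = 0.40 | chance of p ≤ 0.05 |
|---|---|---|---|---|
| 0 | 1.00 | 1.00 | 1.00 | 1–4% |
| 0.25 | 2.00 | 1.58 | 1.38 | 4–25% |
| 0.50 | 3.00 | 2.17 | 1.75 | 8–69% |
| 0.75 | 4.00 | 2.75 | 2.12 | 14–97% |

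The last column is exact enumeration of a two-sided Fisher test in 40 patients, a test assumed here because the plan names none. Its range covers the three values of b and arrhythmia in 3, 8 or 14 patients. These counts correspond to incidences of 8%, 20% and 35%, within the 8–35% that the introduction gives for supraventricular arrhythmias. With 8 against 32 patients, b = 0.30 and r = 0.50, the chance of a significant result is 39%, although arrhythmia predicts nothing by construction.

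**Would it help simply not to count escalations prompted by the recording?** Such escalations occur only in patients with arrhythmia. Suppose they come first and those patients stay in the analysis as event-free. With b = 0.30 and r = 0.50, the counted risk with arrhythmia is 0.30 × (1 − 0.50) = 0.15 against 0.30 without, a spurious ratio of 0.5. The bias is reversed, not removed.

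**The case against.** The strongest reply is that the loop is partly assembled from inference. The explicit statement that clinicians review device data belongs to ASPIRE I. The alert sentence is a general device description and says nothing about PAH therapy. The Background sentence on arrhythmia as a warning sign is hedged and is the hypothesis under study. A reader might infer that the protocol directs clinicians to escalate when an arrhythmia appears; no such rule exists. A reader might also infer that every escalation is counted with its reason unrecorded. The supportable statement is narrower: the endpoint is undefined and no reason is specified. The study chart provides for clinical data collection at each visit, PAH medications are recorded, and no case-report form is among the documents.

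A second reply is that the objective also covers prognosis, and that death or transplantation, functional class, walk distance and NT-proBNP are already listed. This stands. It limits the direct effect to the escalation half of the objective. Transplantation is not fully protected, since it is partly a clinician's decision, and treatment prompted by an arrhythmia could indirectly affect mortality.

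A third reply is that the illustration returns only what is put into it. This also stands: nothing in the documents supports a particular reaction rate, and with no reaction the ratio is 1.0.

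None of these replies supplies a means of separating the two explanations if an association is found.

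**Conclusion.** The concern holds for the escalation half of the ASPIRE III primary objective. If the plan is followed as written, an association between monitored arrhythmia and escalation may be partly self-fulfilling, and the specified data and analysis could not show how much. The size cannot be determined from the documents. Ratios of 1.4 to 4.0 rest wholly on assumed background risks of 20–40% and reaction rates of 25–75%, and show what is possible, not what is expected.

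The conclusion rests on one inference, that the clinicians who can see the device data take part in escalation decisions. This is likely at a single centre recruiting from its own clinic, but it is not stated.

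A reader might go further and infer that the primary objective cannot be answered at all. The documents do not support that: prognosis is a separate part of the objective, and death is not decided by a clinician. The point calls for a change to data capture, analysis and interpretation; it does not invalidate the study.

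**What to change.** Leave clinicians' access to the device data as it is, and make these changes.

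- **Data capture.** At each escalation, record prospectively the date, the reason or reasons (monitor recording, other findings, or both) and whether device data were known at the time.
- **Main analysis.** Include all escalations, with arrhythmia as a time-dependent predictor so that an escalation is never credited to a later arrhythmia. Report escalations by trigger: recording only, mixed, other. Time ordering does not remove the circularity, so this result alone should not support a conclusion that arrhythmia predicts the need for escalation.
- **Sensitivity analysis.** Treat recording-only escalations as a competing event or censor them; do not keep those patients as event-free. State that censoring may be informative.
- **Prognosis.** Rest the conclusion mainly on death and show transplantation separately.
- **Limitations.** State the circularity that remains, including that the reason is recorded by someone who may know the device data.

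The cost is a short addition to the case-report form and a few sentences under Endpoints and Statistical methods. The sensitivity analysis will have fewer events in a study of 40 patients. Many triggers will probably be mixed, since the ASPIRE III Background says that the onset of atrial tachyarrhythmia usually goes with clinical deterioration. The separation will therefore be incomplete.

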Statistical methods	
Repeated measurements of CI, right atrial size, RV size, fibrosis and stroke volume will be performed every 6 months.
 
Two groups of subjects will be defined: 1. Patients with no change in CI, RV size and stroke volume, and 2. A group of patients where one of the measurement change more than 2 standard deviations.
 
It is group-shift (Y/N) if a subject changes out of the 2 stdv band.
 
Time to group shift will be analysed in a subsequent analysis.
 
Cox-model analysis will be done on measurements of (1) cardiac index, (2) RV size, (3) stroke volume and (4) fibrosis to calculate the correlation with risk of developing clinical symptoms and clinical deterioration. In other words, this analysis will establish if the MR-measurements predict clinical outcome.
 
SPSS/PASW Statistics 19 software (SPSS Inc, Chicago IL), SAS or R is used for all statistical analysis.

MRI protocol

Every six months, all subjects are scanned according to the protocol below. The scanning will take 60-80 minutes. MRI scans will be carried out on a 1.5 to 3.0 Tesla MRI scanner. At visit 1, 3 and 5 a cannula will be placed for contrast administration.

MRI studies will provide time-volume curves for LV and RVs filling and ejection fraction, peak emptying rate, peak filling rate and stroke volume will be calculated.

The measurements will provide time-flow curves for flow in the pulmonary trunk, pulmonary branch arteries and aorta. It will be possible to measure the distribution of flow to the right and left lung. Since the pulmonary trunk is often dilated with slow flow, it can be more accurately to measure the flow in the smaller branch pulmonary arteries.

Angiography will also provide the flow distribution in the lungs and the different segments of the lungs.

After baseline scan subjects will be exercised by a MR compatible ergometer with a load of 1 watt per kg. Stress test will measure the physiological reserve in terms of changes in cardiac index and ventricular volumes. Finally, late enhancement will measure the degree of fibrosis in the left and right ventricle.

Scannings protocol		Sekvens
1	Scout	SSFP, single shot
2	Transverse stack, no gaps – covers the hearts	SSFP, 8 mm, 25 phases

ASPIRE: ArrhythmiaS in Pulmonary arterial hypertension and right heart failure assessed by continuous long-term cardiac monitoring

3	LV vertical long axis (VLA)	SSFP, 8 mm, 25 phases
4	Scout LV, short axis	SSFP, single shot

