Release of any information from the patient's journal to the person in charge of the study will take place according to section 46, subsection 1 of the Danish Health Act. According to this section, information about an individual person's health, other private conditions and confidential information in patient journals etc. may be released to a researcher for the use in a concrete biomedical research project. Information about gender distribution, population distribution within various age groups, age distribution, blood pressure and weight may be obtained from a patient's journal. In addition, information may be obtained about symptoms in relation to PAH, medical treatment and possible concomitant diseases. This kind of information may be compared with data appearing from the loop recorder and the MR scans. Any information used for publication will be anonymized.

We adhere to the European regulation on protection of personal data.

The study has been announced to and approved by the Danish Data Protection Agency (J.nr. 2018-41-5331<)

ASPIRE: ArrhythmiaS in Pulmonary arterial hypertension and right heart failure assessed by continuous long-term cardiac monitoring

Financial conditions:

We will apply for funding from external foundations. We will keep The Danish Scientific Ethical Committee currently informed about funding and also notify them when the final funding has taken place.

The study has been started by the initiative of consultant [name]

Recruitment of patients

The patients will be recruited from the cohort already treated at "Kardiologisk Klinik" for PAH. In addition, we will prospectively offer new patients participation in the study and obtain their acceptance.

Publication of test results:

We aim at publishing all results, whether positive, inconclusive or negative, in articles in international scientific journals. Such articles will be found on the internet at www.ncbi.nlm.nih.gov/pubmed by a search on "[name]" and "[name]" and the subject "pulmonary arterial hypertension". If the test results are not accepted by international journals publication of the results will be made in national journals and in presentations at national and international conferences.

Abbreviations

2-DE	2-dimensional echocardiography
6 MWT	6-Minute Walk Test
AF	Atrial Fibrillation
AFL	Atrial Flutter
AVNRT	AtrioVentricular Nodal Reentry Tachycardia
BNP	Brain Natriuretic Peptide
CMR	Cardiac Magnetic resonance imaging

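### ASPIRE III asks whether arrhythmia predicts escalation and prognosis, but its only primary endpoint is arrhythmia itself and no planned analysis links the two

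*Combined protocol and SAP*

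**What the plan says.** In the ASPIRE III synopsis:

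- Study objectives, primary: "To evaluate long-term monitoring of arrhythmias as a predictor tool for escalation of PAH specific therapy and prognosis in patients with PAH".
- Endpoints: the single primary item is "Arrhythmias as assessed by Insertable Cardiac Monitors". The secondary items include "Change and /or escalation of PAH therapy" and death or transplant.
- Statistical methods, complete entry: "SPSS/PASW Statistics 19 software (SPSS Inc, Chicago IL), SAS or R is used for all statistical analysis".

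Elsewhere in the document:

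- ASPIRE I gives as its endpoint "To assess the incidence of arrhythmias in patients with PAH". Its one association analysis reads "Correlation statistics will be done to assess heart rate variability and heart rate in correlation to known risk markers in PH".
- ASPIRE II states "Cox-model analysis will be done on measurements of (1) cardiac index, (2) RV size, (3) stroke volume and (4) fibrosis", to see whether the MR measurements foretell clinical deterioration.
- The section on information from the patient's journal says "This kind of information may be compared with data appearing from the loop recorder and the MR scans". It names no outcome and no method.

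ASPIRE III plans 40 patients followed for 2 years. It gives no derivation of that number.

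**The concern.** In the objective, arrhythmia is the explanatory variable, and escalation and prognosis are what is to be explained. In the endpoint list the explanatory variable has become the primary endpoint, with no summary measure. Reporting it would describe arrhythmia in the cohort, which is ASPIRE I's task, and leave ASPIRE III's own question without a primary result.

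Both outcomes would be collected, but the definition of exposure, the time origin, the model and the effect measure would all be chosen after the data are seen. With few events, the answer can depend heavily on those choices.

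**Working it through.** **1. Does any planned analysis link arrhythmia to the two outcomes?** The plan gives no event rate, effect size, alpha or power for ASPIRE III, so there is no figure to reproduce. This step is a reading of the text.

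| Place | Explanatory variable | Outcome | Fills the gap? |
|---|---|---|---|
| ASPIRE I, Statistical methods | heart rate, heart rate variability | known risk markers | no |
| ASPIRE II, Statistical methods | CMR measurements | clinical symptoms and deterioration | no, arrhythmia is not a predictor |
| ASPIRE III, Statistical methods | none | none | no, software only |
| Information from the patient's journal | none specified | none specified | no, a permissive sentence |

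**2. Is the exposure self-evident?** No. The ASPIRE III Background reports cumulative mortality above 80% with persistent atrial fibrillation, against below 6% with AVNRT or flutter. Conclusions and perspectives says transient episodes seem not to affect mortality. Pooling all types could hide the effect sought.

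**3. What would the simplest analysis give?** Suppose patients who ever had arrhythmia are compared with those who never did, by Cox regression with a fixed covariate. Inputs:

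- Two-year arrhythmia risk 5.5%, 11.7%, 20%, 35% or 60%. The first follows from the 2.8% annual risk in the ASPIRE I Background: 1 − 0.972² = 0.055. The next three are incidences quoted in the background, used here as two-year risks although they are not given as such. The last is assumed, in case continuous monitoring finds more.
- Two-year outcome risk without arrhythmia 15%, 30% or 45% (assumed; not in the documents).
- True hazard ratio after arrhythmia 1 or 2 (assumed).
- Exponential times with hazard λ = −ln(1 − p)/2 per year. For example, 35% gives −ln(0.65)/2 = 0.215 and 30% gives −ln(0.70)/2 = 0.178.

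Results over the grid, with 1,000,000 simulated patients per cell:

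| Arrhythmia counted | True HR 1 | True HR 2 |
|---|---|---|
| only before the outcome (death or transplant) | about 0.35–0.50 | 0.68–0.97 |
| over the full 2 years (escalation) | about 1.0 | about 1.4–1.6 |

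In the 35%/30% cell the first row gives 0.43 and 0.81, the second 1.00 and 1.47.

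In the first row a patient must survive event-free to be classed as having arrhythmia, so the exposed group carries time in which it could not have had the event. In the second row recording continues after escalation, so arrhythmia is counted whether it comes before or after. There is then no bias under the null, but event time before arrhythmia is counted as exposed and the effect is diluted. This row assumes every patient is recorded for the full 2 years.

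**4. What can 40 patients deliver with a time-dependent covariate?** At 5.5%, 40 × 0.055 = 2.2 patients would have an arrhythmia; the chance that none does is 0.972^80 = 10%. Three cells from the same grid, any first arrhythmia as exposure, true hazard ratio 2:

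| Arrhythmia / outcome risk | Events | After arrhythmia | HR not estimable | 95% CI: HR ÷ and × (where estimable) | Power |
|---|---|---|---|---|---|
| 5.5% / 15% | 6.2 | 0.31 | 75% | 9.0 | 9% |
| 35% / 30% | 13.7 | 3.8 | 2% | 3.6 | 22% |
| 60% / 45% | 21.8 | 9.4 | 0% | 2.6 | 31% |

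Power counts a non-estimable study as no finding.

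**The case against.** The best defence is that this is a small observational study, that both outcomes are already listed, and that nothing is lost until the analysis is run. That stands as far as the data go. It does not supply the missing analysis or make arrhythmia an outcome of its own prediction.

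A second objection is that the repaired analysis will be weak at N = 40. That also stands. The power figures are, if anything, generous, because they model any first arrhythmia while the sensible exposure is narrower and rarer. Hence the exploratory label and the priority given to counts and rates.

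Three stronger readings go beyond the documents:

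- A reader might infer that a crude ever/never comparison would hide a doubling of risk for both outcomes. It would for death or transplant. Escalation does not stop the recorder, which works for up to 3 years, so with arrhythmia counted over the full follow-up the effect is diluted and not hidden. The plan does not propose an ever/never comparison at all; the risk arises because no analysis is stated.
- A reader might infer that ASPIRE III admits patients already treated for arrhythmia, since only ASPIRE I excludes them. All three synopses list the same 40 patients by group. If this is one cohort, ASPIRE I's exclusion binds ASPIRE III too. The documents do not settle it.
- A reader might take the shared endpoint with ASPIRE I as an error in itself. It is not; the fault is that it stands alone as primary under a predictive objective.

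**Conclusion.** The point holds and should be corrected before analysis. ASPIRE III's primary endpoint does not answer its primary objective, and no analysis elsewhere closes the gap. This conclusion rests on the text alone and needs none of the simulated figures.

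Those figures show only why the analysis should be fixed in advance and what to expect of it. They depend on assumed outcome risks of 15–45%, assumed hazard ratios of 1 or 2, one outcome range used for both endpoints, and background incidences read as two-year risks for supraventricular arrhythmia.

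**What to change.** Make two outcomes primary for ASPIRE III, both timed from monitor implantation:

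1. time to first escalation of PAH therapy, defined in advance as escalation rather than any change, and censored at death or transplant;
2. time to death or transplant.

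Keep arrhythmia incidence as a descriptive result. Then state the following:

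- **Exposure.** One main arrhythmia exposure, defined in advance by type and duration, entered as a time-dependent covariate and not as ever/never.
- **Reporting.** Event counts and rates per person-year with and without prior arrhythmia, with exact confidence intervals, and a hazard ratio where estimable. A penalised estimate is one option. Label the analysis exploratory.
- **Baseline arrhythmia.** How it is handled, or confirmation that the three sub-studies share one cohort and ASPIRE I's exclusion applies.

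The cost is protocol and SAP wording, plus the date of each PAH therapy change. The visit list records PAH medications but specifies no change date. The reason for each change is worth recording too, because clinicians can review the recordings and the plan does not say whether escalation may follow from them. No extra visit or procedure is needed.

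The downside is wide intervals, low power, and possibly no hazard ratio at all if arrhythmia proves rare.
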